1 INTRODUCTION

1.1 BACKGROUND

Cardiovascular disease remains the main cause of death world-wide ^{1,2,3,4} despite advances in medical therapy ^{5,6,7,8,9,10}. Highly effective preventive regimes are available, but adherence is poor ^{11,12,13,14,15}. There are many causes of non-persistence with medication ¹⁶. Many participants who have indications to receive preventative medication see it as only appropriate for the sick, and – not seeing themselves as sick – seek to avoid medication ^{17,18}. Non-adherence tends to be higher with poor health literacy, lower socioeconomic class ¹⁹ and increasing age ²⁰. Statins reduce cardiovascular event rate by a large proportion ^{21,22,23} but many participants outside trials do not persist with therapy, often because of adverse symptoms that they attribute to the medication. Growing societal suspicion of high adverse event rates in real-life experience is now discouraging even first-time initiation of therapy.

When an adverse symptom is experienced after initiation of a statin, the clinician has a limited repertoire of steps to take. Commonly the drug is stopped and re-tried after an interval with the participant - quite appropriately - advised to bring any recurrence of symptoms to medical attention. In other cases an alternative statin may be tried, with a similar warning to be alert for recurrent symptoms.

Confidential Page 4 of 22

Analysis of the 83,880 participants who have received statins versus placebo in double-blinded randomised placebo controlled trials²⁴ shows no sign of a tendency for greater adverse *symptom* rate on statins versus placebo, if one sets aside increased glucose which is almost never the symptom stated as a reason for stopping statins.

Just as the placebo effect describes a favourable psychobiological effect following the administration of a placebo, the nocebo effect describes the adverse effect a participant experiences through taking a medication, not due to the medication itself. Previous studies quantified the nocebo effect by measuring adverse drug reactions when a placebo is administered and have reported nocebo effects ranging from 19% to $27\%^{25,26,27}$. The nocebo effect is influenced by many factors²⁸, but undoubtedly the information a participant is given about a drug modifies their expectations and therefore their response²⁹. Conditioning from previous negative experience also strongly influences the nocebo effect³⁰.

[figure not shown]

2 STUDY OBJECTIVES

This project will develop, test and deliver a method for this, in the following stages:

- We will develop a method for determining within an individual participant to what extent experienced symptoms are associated with the statin or merely nocebo effect
- 2. We will evaluate in a cohort of participants who have stopped statins because of adverse symptoms, in what proportion of them, the symptoms are truly due to the statin

3 STUDY DESIGN

3.1 PRE-RANDOMISATION EVALUATIONS

A participant and public involvement group have already provided feedback to assist the development of the study proposal. Their feedback is summarised in Appendix 1. The phone application has also been piloted among healthy volunteers and feedback summarized in appendix 2.

3.2 PILOT STUDY: SEMI-STRUCTURED INTERVIEW TO EXPLORE AND MEASURE SYMPTOM EXPERIENCE TO REFINE MEASUREMENT TOOLS FOR THE MAIN TRIAL

Participants: Prior to the trial we will recruit 20 participants who are either 1) currently taking statins with and without adverse symptoms or 2) have previously ceased statin therapy due to adverse symptoms.

Method: The interviews will have two parts. Firstly, we will conduct a brief interview to explore individuals' current or past experience of statins. Secondly, participants will fill out a structured questionnaire that assesses the intensity within each participant of several commonly described statin side-effects, each on a scale of 0-100. These would include muscle aches, fatigue, headache, and gastrointestinal symptoms. In addition, the participants will be asked to complete and comment on the daily and monthly questionnaires planned for the main trial to assess their appropriateness. At the same session participants will have a cognitive interviews to determine their reasoning whilst filling out various different scales. The interviews will be audio-recorded and transcribed using Nvivo software. The exploratory part of the interviews will be interpreted using thematic analysis³² and the cognitive interviews using a content analysis approach³³.

Confidential Page 6 of 22

SAMSON Protocol No: 1.4

Version 1.4 10th April 2020

Scale refinement: The scales used in the main trial will be refined based on the findings from the interviews, and any modifications piloted among further participants.

3.3 RANDOMISED CONTROLLED TRIAL: EVALUATING IN A COHORT OF PARTICIPANTS THE PROPORTION OF ADVERSE SYMPTOMS TRULY DUE TO THE STATIN RATHER THAN THE NOCEBO EFFECT

Participants: 50 participants will be recruited to the trial.

Method: At baseline each participant will have a detailed interview with the study doctor to assess past medical history and previous symptoms attributed to statins and assess if they are eligible to be enrolled. Eligible participants will be enrolled on InForm which will allocate each participant a random predefined order to take the study interventions in. These random codes will be generated by the ICTU statistician and supplied to the production pharmacy. The participant will be dispensed HDPE containers which are in this pre-specified order assigned on inform. Each participant will receive 12 sets of HDPE containers pre-labelled. 4 sets of HDPE containers will contain no medication, 4 will contain 1-month supply of matched placebo and 4 will contain 1-month supply of atorvastatin 20mg. At the start of the next calendar month after the screening visit the participants will commence the trial intervention. The research nurse will call the participant to remind them to start on the 1st day of the next month after screening and thereafter the participants will also receive a monthly reminder on their phone to switch to the next set of HDPE containers each month. Each day participants will rate their daily symptom on a phone application and will also complete 3 additional questionnaires on a monthly basis. The study nurse will call the participant at the end of each month to assess their progress in the trial. Each participants will return their boxes at dispensing visits (if applicable) and at the study end in order for a pill count to be undertaken to assess medication adherence. The placebo and atorvastatin pills will be visually identical.

The study enrols participants not intending to re-start clinical use of statins. Participants' other medications will continue to be managed as normal by their own physicians, with no restriction on starting, stopping or changing doses For safety reasons the participant's own physician will be asked to consult the investigators prior to consideration of starting, or amending the dose of, any other lipid lowering medication

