4 PARTICIPANT ENTRY

4.1 INCLUSION CRITERIA FOR MAIN TRIAL:

- · Aged 18 years or older
- · Previously taken one or more statins
- Withdrawn from statins because of perceived side effects
- Developed side effects within 2 weeks of initiation
- Clinical indication for statins for primary or secondary prevention of cardiovascular disease or dyslipidaemia

4.2 EXCLUSION CRITERIA FOR MAIN TRIAL:

- History of any condition that causes chronic pain
- History of severe mental illness (as their experience of symptoms may already be altered)
- Current taking fibrates (because of the risk of interaction with statins but will not exclude participants taking ezetimibe).
- History of statin intolerance with creatine kinase elevation greater than 5 times the upper limit of normal
- History of statin intolerance with anaphylaxis
- History of statin intolerance with myalgia and rise in serum creatine kinase

Confidential Page 8 of 22

Version 1.4 10th April 2020

- History of statin intolerance with rhabdomyolysis
- History of statin intolerance with liver function abnormalities, defined as aspartate aminotransferase (AST) or alanine aminotransferase (ALT) >3 times the ULN
- · Currently taking antiretrovirals with known interaction to statins
- Currently taking any drug other than antiretrovirals with known interaction to statins
- · Pregnant or breast feeding
- Side effects taking longer than 2 weeks to present (because in such participants much longer blocks of treatment would be required, if the present study is positive such studies will be planned for the future)*
- In clinical judgement of study doctor, participant should not be enrolled on the study

*All participants excluded for this reason will be logged so that the proportion excluded will be known. The study will be explained to consecutive eligible participants, and those giving informed consent will be recruited.

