4.3 WITHDRAWAL CRITERIA

If during the study, participants choose to re-start clinical statin therapy, they will withdraw from the study and start open medication.

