6.2 DRUG ACCOUNTABILITY

Drug accountability logs will be kept for dispensing IMP and for reconciling returned medication. The accountability log will detail:

- Subject identification code
- · Date dispensed
- Dose
- Date of expiry
- · Quantity dispensed
- · Batch number
- Date returned
- Quantity returned
- Recorder's initials

All IMPs should be stored and dispensed by the delegated research staff and managed to the same standards as licensed medicines.

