7 ASSESSMENT AND FOLLOW-UP

Participants will attend a screening visit where the study doctor will receive written informed consent from them if they decide to participate. Then the study doctor will assess the participants eligibility for the study by evaluating their past medical history and previous statin intolerance. Participant's blood pressure will also be measured and if a participant does not have a recent lipid profile recorded in the last 12 months, they will be offered the option of having one undertaken as part of the screening visit. The study doctor will determine if the participant is suitable to be enrolled in the study. If suitable, they will be enrolled on inform.

Unscheduled assessments will not be performed unless participants develop adverse events which the chief investigator considers 'related' to the trial procedure or Atorvastatin therapy.

Scheduled follow-up telephone calls will be undertaken during every month during the 12-month period of the trial. Furthermore, participants scoring will be monitored by study nurse and if they show severe discomfort or if participants are not scoring on their phone unscheduled telephone follow-up calls will be made and if required a unscheduled study visit to see the study doctor and perform unscheduled tests as deemed necessary by the study doctor.

End of study will be defined as when the specified number of patients have been recruited, all patients have completed the 18-month phone interview and the database is locked.

The 12-month follow-up contact may be combined with the end of study visit, if so this would be a face-to-face visit at the study centre or by telephone if the participant is unable to attend in-person during the COVID pandemic. The end of study visit may take place up to 31 days after the 12-month telephone follow-up.

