7.2. Concomitant medications

Information on concomitant medication may be summarized by generic name as reported on the concomitant medication CRF. The number and percentage of subjects who took at least one drug within each generic type will be presented. Subjects will be counted only once if they take the same generic medication more than once.

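### Protocol 3.3 and 4.3 give no consultation or pause rule for newly started non-lipid drugs that the protocol's own product text bars with atorvastatin or allows only with less than 20 mg

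*Protocol*

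**What the plan says.** **Study drug.** Protocol 3.3 (Method) gives each participant four months of atorvastatin 20 mg, four of matching placebo and four with no tablets, in random order.

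**Other drugs during the trial.** Protocol 3.3 says participants' "other medications will continue to be managed as normal by their own physicians, with no restriction on starting, stopping or changing doses". It then asks the participant's own physician, on safety grounds, to consult the investigators before "starting, or amending the dose of, any other lipid lowering medication". No other drug class is named.

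**Entry.** Protocol 4.2 excludes anyone "Currently taking any drug other than antiretrovirals with known interaction to statins", with a parallel exclusion for antiretrovirals. Both describe the position at entry.

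**Withdrawal.** Protocol 4.3 has a single criterion: if during the study "participants choose to re-start clinical statin therapy, they will withdraw from the study and start open medication".

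**Product text.** The summary of product characteristics (SmPC) in Protocol Appendix Four contraindicates glecaprevir/pibrentasvir (SmPC 4.3). It bars systemic fusidic acid with atorvastatin and for 7 days after fusidic acid stops, apart from exceptional cases under close supervision (SmPC 4.4). It says to stop atorvastatin for the fusidic acid course and reports rhabdomyolysis with the combination, some of it fatal (SmPC 4.5). SmPC Table 1 caps atorvastatin at 10 mg daily with tipranavir/ritonavir.

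**Safeguards.** "The study nurse will call the participant at the end of each month to assess their progress in the trial" (Protocol 3.3). Protocol 7 says "Unscheduled assessments will not be performed unless participants develop adverse events which the chief investigator considers" related to trial procedures or atorvastatin. It also has the nurse monitor symptom scores, with unscheduled calls for severe discomfort or missing scores and a doctor visit with tests if required. Protocol 6.1 keeps a current SmPC in the Trial Master File. Under 6.2, study drugs are to be "managed to the same standards as licensed medicines". Code-breaking is covered in 4.4 and 6.4. SAP 7.2 allows other drugs to be summarised "as reported on the concomitant medication CRF".

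**The concern.** The risk from interacting drugs was recognised at entry but is not carried through the 12 months of dosing. The consultation sentence shows that the sponsor saw a need for contact about some new prescriptions, yet it covers only lipid-lowering drugs. Fusidic acid, glecaprevir/pibrentasvir and tipranavir/ritonavir are not lipid drugs. A physician who follows 3.3 to the letter could start one of them during an atorvastatin month without being asked to contact the trial team.

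The gap is more than missing detail: a stated permission in the main text conflicts with the protocol's own appendix. The SmPC is prescribing information. It tells neither an outside physician nor a participant what to do with blinded tablets that may be placebo, and neither 3.3 nor 4.3 points to it. What is at stake is a rare but potentially fatal and preventable muscle injury.

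**Working it through.** The plan states no figure on this point, so the main check sets texts side by side. The counts after it only give scale.

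**1. Texts compared**

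| Drug started mid-trial | SmPC in Appendix Four | Consultation in Protocol 3.3? | Hold or withdrawal in Protocol 4.3? |
|---|---|---|---|
| Systemic fusidic acid | Barred during the course and 7 days after (supervised exceptions) | No | No |
| Glecaprevir/pibrentasvir | Contraindicated | No | No |
| Tipranavir/ritonavir | Atorvastatin at most 10 mg | No | No |

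Trial dose against cap: 20 / 10 = 2. The 20 mg limits with boceprevir and elbasvir/grazoprevir equal the trial dose, so those drugs fall outside the point. So do drugs with advice only to monitor or to lower the dose. SmPC Table 1 is broken in the text available. The cap may also cover telaprevir and ciclosporin, but the point does not need them.

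**2. Would the monthly call come in time?** Assume a call on day 28 of a 28-day month, a course of d days and a uniform start day. The share of courses finished before the call is (28 − d)/28:
- d = 7: 21/28 = 75%
- d = 14: 14/28 = 50%

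For a 30-day month the shares are 23/30 = 77% and 16/30 = 53%. The course lengths are assumptions. Day 28 is one reading: Protocol 3.3 puts the call at month end, while Protocol 7 says only that a call is made during every month.

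**3. Would the barred window meet an atorvastatin month?** With 4 of 12 months on atorvastatin in random order, a window touching k months meets at least one with probability 1 − C(12−k, 4)/C(12, 4), where C(12, 4) = 495:
- k = 1: 1 − 330/495 = 0.333
- k = 2: 1 − 210/495 = 0.576
- k = 3: 1 − 126/495 = 0.745
- k = 4: 1 − 70/495 = 0.859

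Average over the 12 × 28 = 336 possible start days, cutting windows off at trial end:
- 14-day window (7-day course plus 7): 193 starts touch one month and 143 touch two. (193 × 0.333 + 143 × 0.576)/336 = 0.437.
- 21-day window (14-day course plus 7): 116 touch one and 220 touch two. (116 × 0.333 + 220 × 0.576)/336 = 0.492.
- 84-day window (12-week course, assumed): 28, 28, 37 and 243 starts touch one, two, three and four months. The average is 0.779.

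**4. Counts.** The documents give no starting rate. Assume 0.5% to 5% of participants per year, all 60 with 12 months ahead:
- starters: 60 × 0.005 = 0.3 to 60 × 0.05 = 3
- window meeting an atorvastatin month, fusidic acid: 0.3 × 0.437 = 0.13 to 3 × 0.492 = 1.5
- the same for a 12-week course: 0.3 × 0.779 = 0.23 to 3 × 0.779 = 2.3

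These lean high. A one-day overlap counts, the 7-day tail is included, and the SAP of 14 January 2020 already reports 60 randomised, so few would have 12 months left under the protocol of 10 April 2020.

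**The case against.** The strongest reply is that the safety instruction already exists. The SmPC is part of the protocol, says to stop atorvastatin during fusidic acid, and is kept current under 6.1. Outside physicians manage other drugs as they normally would, which includes checking interactions, and asking them about lipid drugs implies that they know of the trial. Information sheets, letters to physicians and SOPs may close the gap. Detection is also better than the monthly call alone suggests: symptoms are scored daily, and severe discomfort prompts a call and, if required, a visit with tests.

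Much of this stands. A reader might infer that the protocol leaves participants unprotected. The documents do not support that, and what the unseen papers say cannot be judged. But daily scoring reacts to harm after it starts, whereas a consultation rule acts beforehand. None of the safeguards in the protocol or SAP tells anyone to hold blinded tablets.

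A reader might also infer that the primary result is biased. Nothing in the documents shows this. Extra symptoms in atorvastatin months would usually enlarge the denominator of the nocebo ratio and so work against Hypothesis 2, and the size cannot be derived.

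A third tempting step is to drop paused days from the primary analysis. That would remove days of illness from tablet months while equivalent days in no-tablet months stayed in. With assumed mean scores of 10 (no tablets), 15 (placebo) and 18 (statin), the ratio is (15 − 10)/(18 − 10) = 5/8 = 0.63. If the no-tablet mean were 1 point higher relative to the others, it would be (15 − 11)/(18 − 11) = 4/7 = 0.57. The 14 and 16 score thresholds in SAP 6.1.1 would not guard against under-recorded symptoms after a restart. They count scores in a month, not days since tablets resumed.

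**Conclusion.** The point holds as a safety improvement that the sponsor should make. For three named treatments, Protocol 3.3 permits what the appended SmPC bars or allows only at half the trial dose, and Protocol 4.3 provides no hold. This rests on the protocol and SAP text alone.

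Events would be rare. Even with a full 12 months ahead for everyone, the assumed rates give between 0.13 and 2.3 participants whose window meets an atorvastatin month, and meeting a month is exposure, not harm. The rate and course lengths are assumptions, so the counts should not carry the argument. Severity and low cost carry it. Sample size, power and the primary estimate are not called into question.

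**What to change.** **Protocol 3.3.** Extend the existing consultation request to drugs that the appended SmPC contraindicates or bars with atorvastatin, or for which it caps atorvastatin below 20 mg. Refer to Appendix Four by name.

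**Protocol 4.3.** State that in any tablet month study tablets are paused, or the participant withdrawn, while such a drug is taken, and for 7 days after the last dose of systemic fusidic acid. The rule covers atorvastatin and placebo months alike. Participants already know which months have no tablets, so no code-break is needed.

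**Analysis.** Leave the primary rule in SAP 6.1.1 unchanged. Record the dates of each pause and, at most, add a sensitivity analysis that leaves out the affected months.

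**Cost.** One short protocol amendment, which helps only participants with tablet months left. Some dosing is lost, including in placebo months where no pause was needed. A fusidic acid course of d days plus 7 inside one 28-day month leaves 28 − 7 − d days of dosing: 14 for a 7-day course, 7 for a 14-day course. Leaving out one month in the sensitivity analysis keeps 3 of 4 for that treatment, and SAP 6.1.1 requires only one. A 12-week course could affect up to four months and would cost more.

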3.4 STUDY OUTCOME MEASURES

For the trial, each participant will receive a smartphone or if preferred can have the application downloaded to their existing phone to allow real-time daily documentation of symptoms experienced on a visual analogue scale of 0-100. Example screen-shots (which will be further refined based on the findings from the pilot study) are shown in Appendix 3. Participants will receive training on the simple touch-screen interface and a leaflet with further information will also be provided. An optional daily reminder can be setup on the participants' phones. Participants will rate symptoms every day, with the daily scores aggregated into a monthly score. This is preferable over scoring only once a month, because participants may struggle to remember and aggregate their symptom burden especially if it varies between days.

Confidential Page 7 of 22

SAMSON Protocol No: 1.4

Version 1.4 10th April 2020

Each month participants will fill out two validated questionnaires on the impact of their side-effects on their quality of life. These are EuroQol (EQ-5D-3L), ³⁴ a well-validated measure of health related quality of life, and the Treatment Satisfaction Questionnaire for Medicine (TSQM) questionnaire, a validated treatment satisfaction questionnaire. EQ-5D-3L assesses five domains of health and overall self-rated health using a visual analogue scale. EQ-5D-3L is conventional for assessing efficacy of medication on quality of life but may not be sufficient for assessing side effects, ³⁵ therefore the TSQM questionnaire will also be used. Use of both a health related quality of life questionnaire and a treatment satisfaction questionnaire will allow assessment of participants' multiple health states, overall self-rated health status and treatment satisfaction, and provide a test of both convergent validity and measurement invariance for the monthly aggregate symptom burden score.

We will also ask participants to fill in a short questionnaire detailing any potentially confounding life events over the previous month e.g. change of daily routine, holidays, bereavement, etc. At the end of study visit, participants will have an exit interview exploring the nature of symptoms occurring during the study in case they may differ from those described in the baseline interview. Participants will also be shown their individual nocebo proportion at the end of study visit. The Participant is then able, as in normal life, to decide to continue on a statin or not. We will follow-up the participants at 6 months after the end of study visit and evaluate:

- a) Whether they are now taking a statin and, if not, the reason
- b) Whether they currently believe that most of the side-effects previously attributed to the statin, were indeed a pharmacological effect of the statin.

